7.1 Efficacy Evaluations

To quantify the subjective benefit using the FACE-Q to determine the patient's satisfaction and comparing it with true objective volume changes measured with the Vectra 3D camera.

8 Statistical Plan

8.1 Primary Endpoint

The primary endpoint is to quantify patient satisfaction with minimally invasive volume correction and to measure the volume metric changes with fillers over time.

8.2 Secondary Endpoints

The secondary endpoints will correlate degree of patient satisfaction with the volumetric measurements from 3-dimensional image analysis.

8.3 Sample Size and Power Determination

The sample size was deemed appropriate to power the study based on previous literature in this area of research.

8.4 Statistical Methods

8.4.1 Baseline Data

Standard descriptive statistics will be used to summarize baseline characteristics and study outcome measures at each visit, both overall, and within each arm.

8.4.2 Efficacy Analysis

The validated FACE-Q will be used to determine patient satisfaction for each arm. The Mirror Software 3D software (Canfield Scientific Inc, Fairfield, New Jersey) will calculate the volumetric changes by comparing the treated area after filler injection to the baseline images. The baseline and post treatment measurements from the Vectra 3D images will determine volumetric changes of the injections over time. All volumetric measurements will be recorded in milliliters, and the average volume change will be calculated. A correlation between patient satisfaction and volumetric changes will be calculated.

CONFIDENTIAL

This material is the property of the University of Pennsylvania.

Statistical tests will be performed as determined by the study team. Mean and standard deviation calculation with regression analysis will be performed for all survey variables. Analysis of variance will also be performed.

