3.1.2 Study Intervention Phase

Intervention will occur during the patient's previously scheduled office visit. The patient will be seen by the PI for the originally scheduled consultation. After the initial consultation, proper screening, and informed consent of the patient is completed the patient will answer one survey and undergo 3-D photography and standard digital photography. After injections the patient will have photographs and the survey administered again before the initial visit is complete.

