3.1.5 Secondary Study Endpoints

- Correlate degree of patient satisfaction with volumetric measurements from 3-D analysis after treatment over the 90 day period

4 Study Population and Duration of Participation

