4.5 Total Number of Subjects and Sites

Total accrual will be 100 patients. The aim will be to enroll all subjects at the University of Pennsylvania Health System (UPHS).

5 Study Intervention

The initial consultation by the principal investigator will determine the injection area and the volume of the injections. Injections of the fillers will be used according to the FDA approval indicated use. All three areas will be injected (nasolabial folds, marionette lines, and lips).

Restylane-L® used for the nasolabial folds and/or marionette lines up to a total of 4 cc (2 cc/side).
Restylane-L® Lyft used for severe nasolabial folds and or marionette lines up to a total of 2 cc (1 cc/side)
Restylane-L® Lyft used for malar deflation will receive up to a total of 4 cc of (2 cc/side)
Restylane® Silk in the lips and cutaneous vermillion used for perioral volume loss will receive up to 1cc per lip.

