6.1.2 Intervention (Day 1)

- If patient is concerned of child bearing potential, a urine pregnancy test will be administered.
- FACE-Q survey will be administered prior to injections
- Photographs with the Vectra 3D camera will be administered prior to injections
- Injections
 - The patient will receive the fillers injectors as suggested in the consultation in all three areas of the face.
- Photographs with the Vectra 3D camera will be administered 30 minutes after injections

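### The planned FACE-Q versus mL correlation fixes neither score form, visit, scale nor volume total and does not use baseline FACE-Q; pre-specify one baseline-adjusted analysis with the change score beside it.

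*Combined protocol and SAP*

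**What the plan says.** The secondary analysis is one sentence in Section 8.4.2: "A correlation between patient satisfaction and volumetric changes will be calculated". Section 8.2 states the endpoint as "The secondary endpoints will correlate degree of patient satisfaction with the volumetric measurements from 3-dimensional image analysis". Section 3.1.5 adds only a time span: "Correlate degree of patient satisfaction with volumetric measurements from 3-D analysis after treatment over the 90 day period".

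The rest of Section 8.4.2 does not narrow this. It says "Mean and standard deviation calculation with regression analysis will be performed for all survey variables", with no outcome, covariate, visit or scale, and "Statistical tests will be performed as determined by the study team". Volume is defined as change in mL from the baseline image, so only the totalling over areas is open.

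Three other places bear on the point:
- Section 5: "The initial consultation by the principal investigator will determine the injection area and the volume of the injections". It says that three areas are injected but also describes malar injection.
- Section 6.1.2: "FACE-Q survey will be administered prior to injections". A baseline score is therefore available.
- Section 3.1.2: "After injections the patient will have photographs and the survey administered again before the initial visit is complete". Section 6.1.2 lists only photographs after injection. With Days 14, 28 and 90 there are thus three or four post-treatment scores, depending on which section is followed.

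**The concern.** Two analysts could both follow Section 8.4.2 and report different correlations from the same data. This matters for two separate reasons.

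First, volume is chosen for each patient and is not randomized. If the choice is related to how satisfied the patient is at baseline, measured mL carries baseline satisfaction with it. A post-score or change-score correlation can then differ from zero although differences in mL do nothing to satisfaction, and the two can point in opposite directions.

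Second, even without such a relation, an open choice among several correlations raises the chance that one of them is significant.

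Section 1.1 wants these data for advising patients and improving treatment. That use invites reading the correlation as the effect of giving more volume.

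**Working it through.** **Inputs.** From the documents: 100 patients (Section 4.5); follow-up at Days 14, 28 and 90 (Section 3.1.3). The documents give no alpha, SD, effect size or correlation (Section 8.3 cites only previous literature), so there is no planned figure to reproduce. Every correlation below is an assumption, as is two-sided 0.05.

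**Algebra.** Let B be baseline FACE-Q, F the post score, V measured mL change, k = SD(F)/SD(B), and p the correlation of V and F given B.

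- r(V,F) = p·√[(1 − rBV²)(1 − rBF²)] + rBV·rBF
- r(V,F−B) = (k·rVF − rBV) / √(1 + k² − 2k·rBF)

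With p = 0, r(V,F) = rBV·rBF, and the numerator of the second formula is rBV·(k·rBF − 1). The slope of F on B is k·rBF. So the expected signs are opposite when three things hold together: rBV is not zero, p = 0, and the slope lies between 0 and 1.

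**Case 1: volume follows baseline FACE-Q.** Assume no volume effect, equal SDs, baseline-post correlation 0.5, and injected-measured correlation 0.65. At a baseline-volume correlation of -0.3:

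- post: -0.3 × 0.5 × 0.65 = -0.098
- change: -0.3 × 0.65 × (0.5 − 1)/√(2 − 2 × 0.5) = +0.098

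Rejection of zero, from 20,000 simulated trials per row:

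| Baseline-volume r | Post score | Change score | Baseline-adjusted |
|---|---|---|---|
| 0 | 5% | 5% | 5% |
| -0.1 | 6% | 6% | 5% |
| -0.2 | 10% | 10% | 5% |
| -0.3 | 16% | 16% | 5% |
| -0.5 | 37% | 36% | 5% |

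At -0.3 the post and change estimates have opposite signs in 68% of trials. At 0 they already do so in about a third, by chance.

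**Case 2: volume follows a stable severity.** Assume no volume effect, severity-baseline correlation -0.5, severity-volume 0.5, injected-measured 0.8 (higher than in Case 1), baseline-post 0.5, and equal SDs. Then rBV = -0.5 × 0.5 × 0.8 = -0.20. For a severity-Day 90 correlation s, post r = s × 0.5 × 0.8 = 0.4s, change r = 0.4s + 0.20, and adjusted r = (0.4s + 0.10)/√(0.96 × 0.75).

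| s | Post r | Change r | Adjusted r |
|---|---|---|---|
| -0.1 | -0.04 | +0.16 | +0.07 |
| -0.25 | -0.10 | +0.10 | 0.00 |
| -0.5 | -0.20 | 0.00 | -0.12 |
| -0.6 | -0.24 | -0.04 | -0.16 |
| -0.7 | -0.28 | -0.08 | -0.21 |

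The slope is 0.5 in every row, yet at s = -0.6 and -0.7 post and change have the same sign, because V is related to F given B. The least biased version also changes from row to row.

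**Case 3: no confounding.** Two score forms by three visits make 6 correlations. If they were independent, the chance of at least one significant result would be 1 − 0.95⁶ = 26%. Simulation (10,000 trials; baseline-post correlation 0.5, visit-to-visit correlation 0.5-0.7 for scores and 0.6-0.9 for mL) gives about 20-25%. With the Day 1 post-injection survey there are 8 correlations and the figure is about 25-30%. Choices of scale and area come on top.

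**Precision.** For a partial correlation near zero with one covariate, the 95% half-width is tanh(1.96/√96) = 0.197.

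**The case against.** The plan promises a correlation and sets no hypothesis or alpha for it. In Case 1 the marginal correlation really is non-zero, so rejecting zero 16% of the time is not an error for that quantity. It is an error only if the result is read as an effect of volume, and an associational label would meet much of that. This stands, and the label is part of the fix. It does not remove the open choices or Case 3, which needs no causal reading.

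All correlations are assumed, and at a baseline-volume correlation of -0.1 the rejection rates are practically nominal. This also stands: the size in this trial is unknown.

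A reader might infer that post-score and change-score results must conflict whenever mL is related to baseline satisfaction. They need not. Case 2 gives agreement at s = -0.6 with no volume effect. A real association can also remove the conflict: with p = 0.2, rBV = -0.2, rBF = 0.5 and equal SDs, the post score gives +0.07 and the change score +0.27.

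A reader might also infer that baseline adjustment is the better method. Case 2 does not bear this out: at s = -0.5 the change score is unbiased and the adjusted one is not, and at s = -0.25 the reverse holds. The documents do not say how volume was chosen in relation to either baseline score or severity, so they support no ranking.

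**Conclusion.** The concern holds in a conditional form. Sections 3.1.5, 8.2 and 8.4.2 leave score form, visit, FACE-Q scale and mL total open and do not use a baseline score that is already collected. If mL is related to baseline satisfaction, either unadjusted version can be non-zero with no volume effect. Opposite expected signs require in addition that volume is unrelated to the post score given baseline and that the slope lies between 0 and 1.

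Under the Case 1 assumptions the false signal ranges from about 6% (baseline-volume -0.1) through 16% (-0.3) to 37% (-0.5), against 5% adjusted. Without any confounding, free choice of score form and visit alone gives about 20-25%. Naming a main analysis matters more than which of the two sound candidates is named. The endpoint is secondary and the primary endpoints are unaffected, so this should be changed but does not threaten the trial.

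**What to change.** In Section 8.4.2, before analysis:

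- Name one main analysis: regression of post-treatment FACE-Q on same-visit total mL change, one record per patient, with pre-injection FACE-Q as covariate, reported as a partial correlation with 95% CI.
- Name one visit (for example Day 90) and treat the other visits as descriptive.
- Name one FACE-Q scale explicitly. Pointing to the primary endpoint is not enough, because no scale is named there either.
- Define total mL as the sum over a stated list of areas, and say whether malar volume is included.
- Report the change-score correlation at the same visit as a pre-specified sensitivity analysis, with its CI. State why both are given: adjustment removes the bias if volume follows baseline FACE-Q, and the change score removes it if volume follows a stable severity with equal effect at both times.
- Draw no conclusion on direction unless both intervals lie on the same side of zero. Comparing signs alone is too loose: with no effect, no confounding and a baseline-post correlation of 0.5, the adjusted and change-score estimates differ in sign by chance in about one trial in six.
- Label the result associational. Agreement of the two estimates does not make it causal.

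Reconcile Section 3.1.2 with Section 6.1.2 on the Day 1 post-injection survey, and the three-area statement in Section 5 with the malar injection described there.

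Cost: SAP wording, one degree of freedom and a few extra results. No new data are needed.

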8.5 Subject Population(s) for Analysis

Per-protocol population: Any eligible patients randomized and adhered with their assigned treatment throughout the course of the trial.

9 Safety and Adverse Events

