5.2 Intervention Regimen

5.2.1 Study Group

The patient will receive the injections of the fillers in all three areas the nasolabial folds, marionette lines, and lips as recommended by the PI during the initial consultation of the regularly scheduled appointment.

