6.4 Subject Withdrawal

Subjects may withdraw from the study at any time without impact to their care. The Investigator may also withdraw subjects who violate the study plan, or to protect the subject for reasons of safety or for administrative reasons. It will be documented whether or not each subject completes the clinical study.

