6.4.1 Data Collection and Follow-up for Withdrawn Subjects

Subjects who withdraw consent to participate in the study may be asked for one final visit or phone interview to collect any study endpoints or adverse events at that time.

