11.1 Risks

All treatments used in this protocol will be used according to the FDA approved intended use. No unexpected risks should occur. Risks that may be experienced from any injection are swelling bruising, redness, itching, infection, or pain.

All HA containing products have the risk of potential tissue loss if there is unrecognized intravascular injection of the fillers. All HA fillers are dissolvable and if you are strongly dissatisfied with the treatment filler or if there is evidence of tissue threat, HA can be removed with hyaluronidase (Vitrase)®. Restylane Silk carries an extra risk of hyperpigmentation to the risks from injection listed above. A risk related to all injectables used in this study is unevenness or lumps.

CONFIDENTIAL

This material is the property of the University of Pennsylvania.

Reproductive risks: If patient is of child-bearing potential, a urine pregnancy test may be administered prior to injection to confirm negative pregnancy status. The effects of this drug/device, there could be serious harm to unborn children or children who are breast-feeding. These effects could also harm the mother.

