11.2 Benefits

Subjects participating in this trial will not directly benefit participating in this study. If assigned to the treatment group, the patient will receive the treatment described in the initial consultation. If assigned to the control group, they may not receive the desired benefits of the requested consultation.

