11.3 Risk Benefit Assessment

Subjects participating in this trial will unlikely experience an increase in risk as both groups receive injections. This study is designed to minimally change patient's care. Subjects participating in this trial are chosen due to the clinic consultation scheduled. No change in patient care will happen if the subject is consented. All subjects will be asked to return for three follow-up visits for observation and surveys.

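### The only analysis set (Section 8.5) requires randomization and adherence to an assigned treatment in a study that describes neither allocation nor arms; it should be all injected patients

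*Combined protocol and SAP*

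**What the plan says.** Section 8.5 lists a single population, labelled per-protocol: "Any eligible patients randomized and adhered with their assigned treatment throughout the course of the trial". There is no all-treated, intention-to-treat or safety set beside it.

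The design sections describe something different. Section 3.1 calls the study prospective and mentions no randomization. Section 5 leaves the injection area and volume to the investigator's consultation. Section 5.2.1 has one Study Group, injected "in all three areas the nasolabial folds, marionette lines, and lips as recommended by the PI". The Study Summary lists the reference therapy as None.

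Words that belong to a multi-arm trial appear elsewhere. Sections 8.4.1 and 8.4.2 and the Study Summary call for results by arm. Section 9.7 dates data storage from the last randomized patient. Section 11.2 says of subjects, "If assigned to the control group, they may not receive the desired benefits of the requested consultation". Section 11.3 says that subjects "will unlikely experience an increase in risk as both groups receive injections".

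On leaving the study, Section 6.4 states: "The Investigator may also withdraw subjects who violate the study plan". Under Section 6.4.1, women who withdraw consent "may be asked for one final visit or phone interview to collect any study endpoints or adverse events at that time". On removal of filler, Section 11.1 says "if you are strongly dissatisfied with the treatment filler or if there is evidence of tissue threat, HA can be removed with hyaluronidase".

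**The concern.** An analysis set has to be a rule that someone can apply to each patient before the results are known. This one cannot be applied as written, because its entry condition is an event that the protocol never schedules. Whoever runs the analysis must decide which words to ignore. Section 8.4.2 leaves the statistical tests to the study team, so that decision could be made after the data are seen.

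Deleting the randomization condition does not complete the repair. What remains is a set of adherers, with no wider population as a check, in a study where satisfaction is a primary endpoint (3.1.4, 8.1). A woman who is unhappy with her result may be more likely to leave or to ask for removal. If either counts as non-adherence, selection into the analysis depends on the outcome being measured.

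**Working it through.** This is mainly a check of definitions, so the conditions in Section 8.5 are set against the rest of the document.

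1. **Randomized.** No section gives a ratio, method, stratification or list of arms. Literal application: patients meeting the condition = 0 of 100.

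2. **Assigned treatment.** Treatment is what the investigator recommends at consultation (5, 5.2.1, 6.1.2). Choice of product is not an allocation either: Section 5 directs Restylane-L Lyft to severe nasolabial folds or marionette lines, so product follows severity.

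3. **Groups.** Section 11.2 has a control group that may miss the desired benefit. Section 11.3 has both groups injected. Neither says what the control receives, and the reference therapy is None. These fragments do not supply the missing allocation.

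4. **Adhered throughout.** Injections are given once, on Day 1 (6.1.2), and follow-up runs to Day 90. The document does not say what adherence means after Day 1. Three cases are unsettled: filler dissolved, fewer than three areas injected, and withdrawal before Day 90.

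5. **Data from women who leave.** Section 6.4.1 allows endpoints to be collected at a final contact, and Section 9.6 keeps information gathered before a revoked authorization usable. Section 8.5 gives no clear basis for analysing either.

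**Size.** The documents give no expected withdrawals, removals or FACE-Q differences, so the bias cannot be derived. Direction and scale can be illustrated. Let k of 100 treated women be left out, with a mean d SD below that of the women retained.

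- Mean of all = mean of retained − (k/100) × d
- Upward shift from exclusion = (k/100) × d

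| k (assumed) | d = 0.5 (assumed) | d = 1 (assumed) |
|---|---|---|
| 5 | 0.025 SD | 0.05 SD |
| 10 | 0.05 SD | 0.10 SD |
| 20 | 0.10 SD | 0.20 SD |

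For scale, the 95% half-width of a mean at n = 100 is t(0.975, 99)/√100 = 1.984/10 = 0.198 SD. Only the last cell reaches it. If the women left out score the same as the rest (d = 0), the shift is zero.

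**The case against.** The best defence is that this is leftover template wording. Treatment is a single session, so on an ordinary reading a woman injected as planned has adhered, and in practice everyone injected would be analysed. No section says that removal counts as non-adherence; Section 11.1 is risk-disclosure language. Sections 5, 5.2.1 and 6.1.2 all require three areas, so a woman treated in fewer would be a protocol deviation and not an expected subgroup. The illustrated shifts rest on assumed inputs and are mostly well below the sampling error.

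Much of that stands, and it limits the claim about bias. It does not rescue the definition. If the intention is to analyse everyone injected, Section 8.5 does not say so, and its condition that adherence last throughout the trial points the other way.

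Three stronger readings are tempting.

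- *A randomized comparison was intended and its details were lost.* The Study Summary speaks of a comparison, Section 2.1 of comparing outcomes, and Section 3.1 of one product or the other. None of these defines arms or allocation, so the document shows neither a randomized trial nor a missing control arm.
- *The plan removes dissatisfied women.* The text leaves this open; it does not order it.
- *The average volume change is distorted by optional malar filler.* Section 8.4.2 says the software "will calculate the volumetric changes by comparing the treated area after filler injection to the baseline images". It names no area, but it does not order pooling and is compatible with measurement by area. Malar filler is also real facial volume, which the secondary objective (2.2) sets out to correlate with patient-reported outcomes. Reporting by area is a preference about detail and is not part of this point.

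**Conclusion.** The point holds for the analysis set. Section 8.5 is the only population defined. Taken literally it admits nobody, and with the randomization condition ignored it restricts both primary analyses to an undefined group of adherers. This follows from the text and needs no assumption.

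Upward bias in satisfaction is a conditional consequence. It requires that women are in fact excluded for leaving or for removal, and that those women are less satisfied. Its size cannot be derived from the documents; the figures above (0.025 to 0.20 SD) are illustrations under assumed inputs. The change is worth making because a better rule is available at almost no cost, not because a large bias has been shown.

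**What to change.** **Section 8.5.** Make the primary analysis set all enrolled patients who received injections, using every available visit. Exclude nobody for filler removal, number of areas treated or later withdrawal. Include endpoints collected under Section 6.4.1. Report the number with data at each visit. Keep any per-protocol set as a sensitivity analysis only, with adherence defined in advance.

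**Elsewhere.** Delete the references to arms (8.4.1, 8.4.2, Study Summary), to the last randomized patient (9.7), and to treatment, control and both groups (11.2, 11.3). If a comparison is intended, define the arms and how patients are allocated to them.

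**Cost.** Rewording only, with no extra visits or images. The number analysed will vary by visit. The change does not recover visits that were never made, so a Day 90 mean still rests on the women seen then; the counts by visit let a reader judge how far that matters.
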